7.1.1.2 Recommended Telephone Call (Day -7 to -4)

Approximately 4 to 7 days prior to the Baseline Visit (Visit 2), it is recommended that site staff telephone the subject or the subject's caregiver to remind them to enter UC-DAI symptoms (rectal bleeding and stool frequency) into the e-diary every night, even if the subject has no symptoms.

7.1.1.3 Baseline Visit (Visit 2)

The Baseline visit will take place 3 to 21 days after the first day of the Screening Visit (Visit 1) to allow blood and stool tests to be analyzed, and for collection of e-diary data. An extension to this 3- to 21-day period is allowed only in the case where a repeat endoscopy will be performed during the period of the Screening Visit (Visit 1) (see Section 7.1.1.1).

The ± 3 -day visit window which is applicable to other study visits is not applicable to this visit.

The partial UC-DAI score will be calculated by the site, and the mucosal appearance (endoscopy score) will be evaluated separately to determine eligibility for either the Double-blind Acute Phase or the Double-blind Maintenance Phase. The following criteria will determine the study phase a subject can be eligible to enter:

- Subjects with partial UC-DAI ≥ 2 (with a combined rectal bleeding **and** stool frequency score ≥ 1 **and** PGA=1 or 2) **and** with mucosal appearance (endoscopy score)=2 or 3 will be eligible to enter the Double-blind Acute Phase.

- Subjects with partial UC-DAI ≤ 1 (with rectal bleeding=0 **and** stool frequency ≤ 1 **and** PGA=0) **and** with mucosal appearance (endoscopy score)=0 or 1 will be eligible to enter the Double-blind Maintenance Phase.

Subjects with partial UC-DAI score between 1 and 2 will not be eligible to enter the Double-blind Acute Phase or the Double-blind Maintenance Phase.

Subjects who do not meet all the eligibility criteria for either the Double-blind Acute Phase or the Double-blind Maintenance Phase will be considered screen failures. Subjects may be rescreened after consultation with the medical monitor.

A minimum of 1 score each for stool frequency and rectal bleeding must be available in order to randomize subjects into either the Double-blind Acute Phase or the Double-blind Maintenance Phase (see Section [7.2.1.1](#) for details). Subjects with no symptom score data available will be considered screen failures as these symptom score data are used to calculate the partial UC-DAI score needed for enrollment.

Subjects with a historical diagnosis of UC:

Endoscopy (flexible sigmoidoscopy or colonoscopy) must be performed at the Baseline Visit (Visit 2) if not performed at the Screening Visit (Visit 1) or within 21 days prior to the Screening Visit (Visit 1) (21 days prior applicable only to subjects entering into the Double-blind Acute Phase directly). Endoscopic video or photographs will be collected and sent to the study's central endoscopy reader for evaluation of mucosal appearance.

Please see a description of criteria used for endoscopic scoring in [Appendix 2](#).

If the results of blood and stool tests or partial UC-DAI score show that the subject is not eligible for the study, he/she will not continue in the study and will be considered a screen failure. No additional data will be captured for these subjects.

Eligible subjects will be randomized to low- or high-dose MMX mesalamine/mesalazine stratified by their weight group at the Baseline Visit (Visit 2). If a subject's weight changes during a study phase, their dose will not change.

Weight groups have the same absolute low and high doses for both the Double-blind Acute Phase and the Double-blind Maintenance Phase (see Section [6.2.3](#)).

Double-blind investigational product will be dispensed to eligible subjects per the procedures detailed in Section [6](#).

Subjects and/or caregivers will be instructed to collect UC-DAI symptoms (rectal bleeding and stool frequency) via e-diary once a day before bedtime for 5 days prior to each study visit in the Double-blind Acute Phase and/or Double-blind Maintenance Phase as applicable. The average stool frequency and rectal bleeding scores will be calculated and be made available to the investigator through a report from the e-diary provider. The average stool frequency and rectal bleeding scores will be added to the PGA score determined by the investigator to calculate the partial UC-DAI. Please see a description of the PGA in Section [7.2.1.1](#) and the UC-DAI in Sections [7.2.1.1](#) and [7.2.1.2](#).

Subjects and/or caregivers will be instructed to complete the DUCS and the Overall Current Health e-diary once a day before bedtime for 5 days prior to each study visit in the Double-blind Acute Phase or Double-blind Maintenance Phase as applicable.

The IMPACT III questionnaire will be completed by children aged 8-17 years via paper at the Baseline Visit (Visit 2). Please see a description of the IMPACT III questionnaire in Section [7.2.4.1](#).

The PUCAI score will be calculated by a physician at the site, where applicable. Please see a description of the PUCAI in Section [7.2.4.1](#).

See [Table 1](#) and [Table 3](#) for a listing of all Baseline Visit (Visit 2) procedures.

7.1.1.4 Subject Visit Schedule Summary Post-baseline

Following the Baseline Visit (Visit 2), subjects will proceed through the study in 1 of 3 ways.

1. Double-blind Acute Phase → Open-label Acute Phase → Double-blind Maintenance Phase.

Visits completed post-Baseline Visit (Visit 2) are as follows: Visit 3, Visit 3.1, Visit 3.2, Visit 4, Visit 4.1, Visit 4.2, Visit 5, Visit 5.1, Visit 5.2, and Visit 6.

Note that Visit 3.1 and/or Visit 3.2 may not be completed in the case that a subject enters into the Open-label Acute Phase without completing the Double-blind Acute Phase. See Section [7.1.3](#) for the criteria for subject eligibility to enter the Open-label Acute Phase.

2. Double-blind Acute Phase → Double-blind Maintenance Phase.

Visits completed post-Baseline Visit (Visit 2) are as follows: Visit 3, Visit 3.1, Visit 3.2, Visit 5, Visit 5.1, Visit 5.2, and Visit 6.

3. Double-blind Maintenance Phase only.

Visits completed post-Baseline Visit (Visit 2) are as follows: Visit 5, Visit 5.1, Visit 5.2, and Visit 6.

7.1.2 Double-blind Acute Phase

7.1.2.1 Recommended Telephone Call (Day -7 to -4)

Approximately 4 to 7 days prior to the Baseline Visit (Visit 2) and prior to each subsequent visit (Visits 3, 3.1, and 3.2), it is recommended that site staff telephone the subject or the subject's caregiver to remind them to enter UC-DAI symptoms (rectal bleeding and stool frequency) into the e-diary every night, even if the subject has no symptoms.

7.1.2.2 Double-blind Acute Phase Weeks 2 and 4 (Visits 3 and 3.1, respectively)

Subjects and/or caregivers will collect UC-DAI symptoms (rectal bleeding and stool frequency) via e-diary and will complete the DUCS and the Overall Current Health e-diary once a day before bedtime for 5 days prior to each study visit in the Double-blind Acute Phase.

The PGA score will be determined by the investigator. Please see a description of the PGA in Section [7.2.1.1](#).

The Global Change in Health questionnaire will be completed via paper at Visits 3 and 3.1. Please see a description of the Global Change in Health questionnaire in Section [7.2.4.1](#).

See [Table 1](#) for a listing of all Visit 3 and Visit 3.1 procedures.

7.1.2.3 Double-blind Acute Phase Week 8/Withdrawal (Visit 3.2)

The Double-blind Acute Phase Withdrawal Visit may occur at any time the subject discontinues participation in the Double-blind Acute Phase, or at completion of the study at Week 8 of the Double-blind Acute Phase. No additional Baseline Visit is required for subjects continuing into the Open-label Acute Phase or the Double-blind Maintenance Phase from this visit.

Subjects with a clinical response ie, partial UC-DAI ≤ 1 (with rectal bleeding=0 **and** stool frequency ≤ 1 **and** PGA=0) will be weighed and re-randomized into the Double-blind Maintenance Phase for treatment with low- or high-dose MMX mesalamine/mesalazine stratified by weight group based on current weight. Please see Section [6.2.3](#) for weight-stratified randomization groups. Subjects without a clinical response may continue into the Open-label Acute Phase and receive MMX mesalamine/mesalazine at the high dose for their weight group, based on their weight at Visit 3.2 (Week 8/Withdrawal of the Double-blind Acute Phase).

Collection of stool samples for all assessments must occur before administration of any bowel preparations for endoscopy if samples are collected on the same day as bowel preparation administration.

Endoscopy (flexible sigmoidoscopy or colonoscopy) should be performed at Visit 3.2 for subjects who are not entering into the Open-label Acute Phase. If performed, endoscopic video or photographs will be collected and sent to the study's central endoscopy reader for evaluation of mucosal healing. Please see a description of criteria used for endoscopic scoring in [Appendix 2](#). If endoscopy is not performed at Visit 3.2 and the subject is otherwise eligible, the subject may remain in the study.

Subjects and/or caregivers will have collected UC-DAI symptoms (rectal bleeding and stool frequency) via e-diary once a day before bedtime for 5 days prior to each study visit in the Double-blind Acute Phase. The average stool frequency and rectal bleeding scores will be calculated and be made available to the investigator through a report from the e-diary provider. The average stool frequency and rectal bleeding scores will be added to the PGA score determined by the investigator to calculate the partial UC-DAI. Please see a description of the PGA in Section [7.2.1.1](#) and the UC-DAI in Sections [7.2.1.1](#) and [7.2.1.2](#).

The IMPACT III (for children aged 8-17 years) and Global Change in Health questionnaires will be completed via paper at Visit 3.2. Please see a description IMPACT III and Global Change in Health questionnaires in Section [7.2.4.1](#).

The PUCAI score will be calculated by a physician at the site, where applicable. Please see a description of the PUCAI in Section [7.2.4.1](#).

A pharmacokinetic sample will be taken with the biochemistry and hematology sample from subjects at sites qualified for and participating in the pharmacokinetic sampling. Please see a description of the pharmacokinetic sampling in Section [7.2.3](#).

See [Table 1](#) for a listing of all Visit 3.2 procedures.

7.1.3 Open-label Acute Phase

Subjects may enter the Open-label Acute Phase after completion of the Double-blind Acute Phase if they do not meet the requirements for entry into the Double-blind Maintenance Phase ie, they do not achieve a clinical response defined as a partial UC-DAI ≤ 1 (with rectal bleeding=0 *and* stool frequency ≤ 1 *and* PGA=0). This phase is intended to allow those subjects without clinical response in the Double-blind Acute Phase an additional 8 weeks to achieve clinical response at the high dose for their weight group. The subject's weight at Visit 3.2 (Week 8/Withdrawal of the Double-blind Acute Phase) will be used to determine the high dose assigned to the subject in the Open-label Acute Phase.

Subjects are also eligible for the Open-label Acute Phase provided they have participated in the Double-blind Acute Phase for a minimum of 2 weeks and, in the investigator's opinion, have not benefited from treatment in the Double-blind Acute Phase. In addition, they should not have experienced a possibly or probably related severe adverse event (AE) or a serious AE (SAE). Due to the delay in onset of action of 5-ASA preparations, investigators should make subjects/caregivers aware that they may not benefit from the investigational product within the first 2 weeks. Subjects who withdraw before Visit 3 will not be eligible for the Open-label Acute Phase.

7.1.3.1 Recommended Telephone Call (Days -7 to -4)

Approximately 4 to 7 days prior to Visit 4 and prior to each subsequent visit (Visits 4.1 and 4.2), it is recommended that site staff telephone the subject or the subject's caregiver to remind them to enter UC-DAI symptoms (rectal bleeding and stool frequency) into the e-diary every night, even if the subject has no symptoms.

7.1.3.2 Open-label Acute Phase Weeks 2 and 4 (Visits 4 and 4.1, respectively)

Subjects and/or caregivers will collect UC-DAI symptoms (rectal bleeding and stool frequency) via e-diary and will complete the DUCS and the Overall Current Health e-diary once a day before bedtime for 5 days prior to each study visit in the Open-label Acute Phase.

See [Table 2](#) for a listing of all Visit 4 and 4.1 procedures.

7.1.3.3 Open-label Acute Phase Week 8/Withdrawal (Visit 4.2)

The Open-label Acute Phase Withdrawal Visit may occur at any time the subject discontinues participation in the Open-label Acute Phase, or at completion of the study at Week 8 of the Open-label Acute Phase. No additional Baseline Visit is required for subjects continuing into the Double-blind Maintenance Phase from this visit.

Subjects with a clinical response, ie, partial UC-DAI ≤ 1 (with rectal bleeding=0 **and** stool frequency ≤ 1 **and** PGA=0) will be weighed and re-randomized into the Double-blind Maintenance Phase of the study for treatment with low- or high-dose MMX mesalamine/mesalazine stratified by the weight group based on current weight. Please see Section 6.2.3 for weight-stratified randomization groups.

Subjects without a clinical response after completion of the Open-label Acute Phase will be withdrawn from the study at Visit 4.2. The Follow-up Visit 6 must be conducted.

Collection of stool samples for all assessments must occur before administration of any bowel preparations for endoscopy if samples are collected on the same day as bowel preparation administration.

Endoscopy (flexible sigmoidoscopy or colonoscopy) should be performed at Visit 4.2. If performed, endoscopic video or photographs will be collected and sent to the study's central endoscopy reader for evaluation of mucosal healing. Please see a description of criteria used for endoscopic scoring in [Appendix 2](#). If endoscopy is not performed and the subject is otherwise eligible at Visit 4.2, the subject may remain in the study.

Subjects and/or caregivers will have collected UC-DAI symptoms (rectal bleeding and stool frequency) via e-diary once a day before bedtime for 5 days prior to each study visit in the Open-label Acute Phase. The average stool frequency and rectal bleeding scores will be calculated and be made available to the investigator through a report from the e-diary provider. The average stool frequency and rectal bleeding scores will be added to the PGA score determined by the investigator to calculate the partial UC-DAI. Please see a description of the PGA in Section 7.2.1.1 and the UC-DAI in Sections [7.2.1.1](#) and [7.2.1.2](#).

The PUCAI score will be calculated by a physician at the site, where applicable. Please see a description of the PUCAI in Section [7.2.4.1](#).

A pharmacokinetic sample will be taken with the biochemistry and hematology sample from subjects at sites qualified for and participating in the pharmacokinetic sampling. Please see a description of the pharmacokinetic sampling in Section [7.2.3](#).

See [Table 2](#) for a listing of all Visit 4.2 procedures.

7.1.4 Double-blind Maintenance Phase

7.1.4.1 Recommended Telephone Call (Days -7 to -4)

Approximately 4 to 7 days prior to the Baseline Visit (Visit 2) and prior to each subsequent visit (Visits 5, 5.1, and 5.2), it is recommended that site staff telephone the subject or the subject's caregiver to remind them to enter UC-DAI symptoms (rectal bleeding and stool frequency) into the e-diary every night, even if the subject has no symptoms.

7.1.4.2 Double-blind Maintenance Phase Weeks 2-4 (Visit 5)

Subjects and/or caregivers will return to the study site once between 2-4 weeks after randomization into the Double-blind Maintenance Phase.

The purpose of this visit is to dispense additional investigational product. Unused investigational product and empty/used investigational product packaging will be collected.

The subject does not need to be present for this visit; it is sufficient for the caregiver only to return to the study site for investigational product dispensation and collection procedures.

No study procedures other than investigational production dispensation and collection are performed at Visit 5; however, if information is offered by the subject or caregiver that indicates an AE has occurred, the relevant information will be collected and followed up as described in Section 8.

See [Table 3](#) for a listing of all Visit 5 procedures.

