^b Subjects will continue into the Double-blind Maintenance Phase if partial UC-DAI ≤ 1 (with rectal bleeding=0 **and** stool frequency ≤ 1 **and** PGA=0) and are eligible to continue into the Double-blind Maintenance Phase.

^c Subjects will be withdrawn from the study if they have not achieved a partial UC-DAI ≤ 1 (with rectal bleeding=0 **and** stool frequency ≤ 1 **and** PGA=0).

^d This will be the final visit for subjects not continuing into the Double-blind Maintenance Phase.

^e The Baseline Visit (Visit 2) does not need to be repeated for subjects entering the Double-blind Maintenance Phase at the end of the Open-label Acute Phase. Visit 4.2 will be considered the Week 0 visit for the Double-blind Maintenance Phase.

^f Follow-up assessment in this phase applies only to subjects who are discontinuing the study; may be performed via telephone call within 7 days of the last dose of investigational product.

^g A visit window of ± 3 days is permitted for all study visits.

^h The serum pregnancy test will be performed for all female subjects of childbearing potential at Week 8/Withdrawal (Visit 4.2). Urine pregnancy tests will be performed at all other visits.

ⁱ Rectal bleeding, stool frequency, DUCS, and Overall Current Health e-diary entry is completed once a day before bedtime every day for 5 days immediately prior to Visits 4, 4.1 and 4.2 of the Open-label Acute Phase.

^j The average stool frequency and rectal bleeding scores will be calculated and available to the investigator through a report from the e-diary provider.

^k Components of the partial UC-DAI.

^l Components of the modified full UC-DAI.

^m Only for subjects continuing into the Double-blind Maintenance Phase.

Table 3: Double-blind Maintenance Phase

Visit	1 (Screening) ^a	Recommended Telephone call ^b	2 (Baseline) ^a	5	5.1	5.2	6 ^c
Day/Month^d	Day -21 to -3	Day -7 to -4	Week 0	Weeks 2-4	Week 13	Week 26/ Withdrawal	Follow-up
Informed consent	✓						
Inclusion/exclusion criteria	✓		✓				
Demographics	✓						
Medical and medication history	✓						
Physical examination	✓				✓	✓	
Height	✓						✓
Weight	✓		✓				✓
Vital signs	✓		✓		✓	✓	
Biochemistry (includes C-reactive protein) and hematology	✓						✓
Pregnancy test (for females of childbearing potential only) ^e	✓		✓	✓	✓	✓	
Pharmacokinetic blood sampling (at participating sites only)						✓	
Urinalysis	✓					✓	
[REDACTED]				✓			
[REDACTED]	✓						
Stool sample (culture) ^{f,g}	✓						
[REDACTED]	✓					✓	

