^d A visit window of ± 3 days is permitted for all study visits except for the Screening Visit (Visit 1) (must be 3 to 21 days) and the Baseline Visit (Visit 2), which must occur 3 to 21 days following the Screening Visit (Visit 1). If the initial endoscopy is not adequate for mucosal healing score assignment due to inadequate bowel preparation, to allow for a repeat endoscopy to be conducted, the period of the Screening Visit (Visit 1) can be extended by an additional 14 days from the date of the initial endoscopy.

^e The serum pregnancy test will be performed for all female subjects of childbearing potential at the screening visit (Visit 1) and Week 26/Withdrawal (Visit 5.2). Urine pregnancy tests will be performed at all other visits.

^f [REDACTED]
Stool samples collected for culture may be processed by local laboratories in addition to the assessment by the central laboratory. Central laboratory results will prevail and, as such, they will be the data entered into the eCRF.

^h Rectal bleeding, stool frequency, DUCS and Overall Current Health e-diary entry is completed once a day before bedtime every day during the Screening Visit (Visit 1), preferably for at least the 3 days immediately prior to the Baseline Visit (Visit 2). Rectal bleeding, stool frequency, DUCS and Overall Current Health e-diary entry is completed once a day before bedtime for the 5 days immediately prior to Visit 5.1 and Visit 5.2.

ⁱ Global Change in Health to be completed by caregivers of children aged 5-10 years and by children aged 11-17 years; IMPACT III to be completed by children aged 8-17 years only.

^j The average stool frequency and rectal bleeding scores will be calculated and available to the investigator through a report from the e-diary provider.

^k Components of the partial UC-DAI.

^l Components of the modified full UC-DAI.

^m For subjects entering the Double-blind Maintenance Phase directly: Subjects with a previously confirmed diagnosis must have endoscopy at the Screening Visit (Visit 1) or at the Baseline Visit (Visit 2). If the initial endoscopy is not adequate for mucosal healing score assignment due to inadequate bowel preparation, to allow for a repeat endoscopy to be conducted, the period of the Screening Visit (Visit 1) can be extended by an additional 14 days from the date of the initial endoscopy.

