7.2.2.7 Pregnancy Test

A serum β -HCG pregnancy test is performed for all females of childbearing potential at the following visits as applicable to the subject's participation in the study:

- Screening Visit (Visit 1)
- Double-blind Acute Phase: Week 8 (Visit 3.2)
- Open-label Acute Phase: Week 8 (Visit 4.2)
- Double-blind Maintenance Phase: Week 26 (Visit 5.2)
- If pregnancy is suspected
- On withdrawal of the subject from the study.

A urine pregnancy test is performed for all females of childbearing potential at all other visits as indicated in [Table 1](#), [Table 2](#), and [Table 3](#).

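### For females of childbearing potential, Protocol 7.1.4.2 limits Maintenance Visit 5 to product exchange, while Table 3, Section 7.2.2.7 and the SAP require a urine pregnancy test there

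*Protocol*

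**What the plan says.** Protocol 7.1.4.2 treats Visit 5 (Weeks 2-4 of the Double-blind Maintenance Phase) as a supply visit: "No study procedures other than investigational production dispensation and collection are performed at Visit 5". On attendance it says "The subject does not need to be present for this visit; it is sufficient for the caregiver only to return to the study site". Adverse events are followed up only "if information is offered by the subject or caregiver that indicates an AE has occurred". The section closes by sending the reader to Table 3 "for a listing of all Visit 5 procedures". The visit list in the synopsis, and Sections 7.1.4.3 and 7.1.4.4, also describe Visit 5 as product-only.

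Table 3 contains a row headed "Pregnancy test (for females of childbearing potential only"), with a tick under Visit 5. Footnote e assigns serum tests to Visits 1 and 5.2 and adds: "Urine pregnancy tests will be performed at all other visits". Section 7.2.2.7 gives the same rule: "A urine pregnancy test is performed for all females of childbearing potential at all other visits as indicated in" the three schedule tables. SAP 4.4.5 and SAP Table 7, with its own footnote e, match. Table 3 also ticks an adverse event assessment at Visit 5.

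**The concern.** For a female of childbearing potential, a site cannot follow both sets of instructions as written. Section 7.1.4.2 excludes any procedure beyond product exchange and says she may stay at home; the schedule says she has a urine test. Neither document states which text takes precedence.

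The stake is pregnancy monitoring in minors on study drug. Section 8.1.6 requires a pregnant participant to be withdrawn. A site relying on the visit narrative could miss a scheduled test, dispense the supply that carries the subject to Week 13, and incur a deviation against Table 3. The attendance permission matters most, because families act on it before the visit. If the caregiver arrives alone and no arrangement for a sample was made, consulting Table 3 at that point is too late for that visit.

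**Working it through.** **Side-by-side reading for Visit 5**

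| Source | Pregnancy test at Visit 5? | Subject needed? |
|---|---|---|
| Protocol 7.1.4.2 | No: product exchange only | No |
| Protocol synopsis, 7.1.4.3, 7.1.4.4 | No: product only | Not addressed |
| Protocol Table 3 and footnote e | Yes, urine | Not addressed |
| Protocol 7.2.2.7 | Yes, urine, through Table 3 | Not addressed |
| SAP 4.4.5, SAP Table 7 and footnote e | Yes, urine | Not addressed |

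**Is the tick genuine?** Some Table 3 rows appear shifted in the extracted text (height and weight, for example), so the row was checked in two ways. Against the column order Visit 1, telephone call, 2, 5, 5.1, 5.2, 6, the pregnancy row reads tick, blank, tick, tick, tick, tick, blank in both Protocol Table 3 and SAP Table 7. Separately, footnote e gives urine tests to every visit other than 1 and 5.2, which includes Visit 5. The two checks agree.

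**Intervals between scheduled tests**, in days from Maintenance Week 0. A test falls at Week 0 by either route of entry: Visit 2 for direct entrants, Visit 3.2 or 4.2 for those rolling over.

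- Visit 5: 2 × 7 = 14 to 4 × 7 = 28
- Week 13: 13 × 7 = 91
- Week 26: 26 × 7 = 182

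| | Following Table 3 | Following 7.1.4.2 |
|---|---|---|
| Week 0 to next test | 14-28 | 91 |
| Visit 5 to Week 13 | 91 − 28 = 63 to 91 − 14 = 77 | no Visit 5 test |
| Week 13 to Week 26 | 182 − 91 = 91 | 91 |
| Tests after Week 0 | 3 (Visits 5, 5.1, 5.2) | 2 (Visits 5.1, 5.2) |

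The longest scheduled interval in the phase is 91 days either way. The ±3-day window in Table 3 footnote d turns the 91 days from Week 0 to Week 13 into 88-94 and does not alter the comparison. Drug dispensed at Visit 5 has to last the same 63-77 days until Week 13.

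**The case against.** The strongest reply is that the intended rule is easy to find. Section 7.1 sends sites to Tables 1 to 3 for procedures, and 7.1.4.2 ends by naming Table 3. The product-only sentence is evidently shorthand, since Table 3 also ticks IRT entry and a compliance calculation at Visit 5. The Amendment 5 change summary points the same way, recording that urine tests were added for all site visits. All of this stands and makes omission less likely. It does not remove the conflict: the section contradicts the table it cites, the product-only description recurs in three other places, and the permission to stay at home is explicit.

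A second reply is that no harm is shown. The schedule already accepts 91 days between Week 13 and Week 26, Section 4.4.1 requires contraception, and Section 7.2.2.7 calls for a serum test when pregnancy is suspected. This also stands, and it keeps the point small.

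A reader might go further and infer that caregiver-only attendance makes the test impossible. The documents do not support that. They say the test is performed at the visit, but nothing bars a caregiver from bringing a sample. The accurate statement is that the protocol does not say how the test is done when the subject is absent.

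**Conclusion.** The inconsistency is real and lies in current text. It is confined to females of childbearing potential; nothing suggests that other subjects need a test at Visit 5. At stake is one scheduled urine test per such subject, and a first interval of 91 days instead of 14-28 followed by 63-77. The documents do not say how many of the at least 80 Maintenance subjects this covers.

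This is a low-priority correction. A reader might infer that the test will be missed, or that the phase loses its tightest safeguard against late detection. Neither follows: omission is possible, not certain, and the longest untested interval does not change. The efficacy analyses do not depend on it. The day counts assume nominal visit timing.

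There is a minor related mismatch. Section 7.1.4.2 takes adverse event information only if it is volunteered, whereas Table 3 ticks the assessment and Section 7.2.2.4 calls for questioning at each study visit. The consequence is small, because Table 3 also ticks adverse events at the recommended telephone calls and the Week 13 questions reach back to the previous visit.

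**What to change.** Amend four places in the protocol: Section 7.1.4.2, the synopsis visit list, and the product-only clauses in Sections 7.1.4.3 and 7.1.4.4. The revised text should say that females of childbearing potential attend Visit 5 for the urine test already in Table 3, and that a caregiver alone is sufficient for all other subjects. In the same edit, have whoever attends asked about adverse events. Table 3, Section 7.2.2.7 and the SAP need no change.

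If the sponsor would rather keep caregiver-only attendance for everyone, the text would have to state expressly that the caregiver may bring a sample. Attendance in person is the simpler rule.

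The cost is wording plus the sponsor and IRB/EC approval that Section 10.3.2 requires for amendments; it could travel with any other amendment. The practical downside is that some adolescent females must come to a visit that 7.1.4.2 now lets them skip. No new procedure is introduced.
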